9.3. Vital Signs

Descriptive summaries of observed values and changes from baseline will be presented for systolic blood pressure, diastolic blood pressure, heart rate, and temperature which will be measured at the following visits.

Screening Period, Baseline (Study Day 1), Week 4, Week 16, Week 28, Week 40, and Week 52/ET/ED.

Body weight will be summarized descriptively in the tabulations for the visits at which it will be measured.

Body Mass Index (BMI): Baseline BMI results will be used from vital sign page in EDC and post baseline BMI results will be derived using post baseline body weights at each visit and screening height. A visit wise descriptive summary and change from baseline analysis of BMI will be provided.

Formula for BMI = weight in kg/ (height in metre)².

All vital signs results will be listed.

9.4. Standard 12-lead ECG

12-lead ECGs will be performed at the following visits:

Screening Period, Baseline (Study Day 1), Week 4, Week 28, and Week 52/ET/ED.

12-lead ECG readings will be obtained using an ECG machine that automatically calculates the heart rate and measures PR interval, QRS interval, RR interval, QT interval, QTcB interval (corrected QT according to Bazett), and QTcF interval (corrected QT according to Fridericia). All scheduled ECGs should be performed after the participant has rested quietly for at least 5 minutes in a supine position.

12-lead ECGs will be performed in triplicate at Baseline (Study Day 1) and thus the triplicates will be averaged for the summaries.

The ECG results will be interpreted as 'Normal', and 'Abnormal, Not Clinically Significant (NCS)', and 'Abnormal, Clinically Significant (CS)'.

The overall assessment by treatment group will be summarized at each timepoint using number and percent of participants.

For Heart Rate (beats/min), PR interval (msec), RR Interval (msec), QRS Interval (msec), QT Interval (msec), QTcF (msec), QTcB (msec), the observed and change from baseline data will be descriptively summarized by treatment group showing the number of observations (n), mean, SD, median, minimum, and maximum value.

The number and percentage of participants having observed QT, QTcB and QTcF values that satisfy the following conditions will be summarized:

- ≤ 450 msec
- > 450 to ≤ 500 msec
- > 500 msec

The number and percentage of participants having change from baseline QT, QTcB and QTcF values that satisfy the following conditions will be presented:

- ≤ 0 msec
- > 0 to ≤ 30 msec
- > 30 to ≤ 60 msec

- > 60 msec

All ECG findings will be listed.

9.5. Further Safety Evaluations

9.5.1. Physical Examinations

A **complete** physical examination will include the body systems: Skin, Head, Ears, Eyes, Nose, Throat, Neck/Thyroid, Lymph Nodes, Cardiovascular, Respiratory, Abdomen, Musculoskeletal, Extremities, and Other; and it will be performed at the Screening visit only. All participants with ‘Normal’, ‘Abnormal, Not Clinically Significant (NCS)’, and ‘Abnormal, Clinically Significant (CS)’ physical exam (complete) findings will only be listed.

A **brief** physical examination will include the body systems: general appearance, Cardiovascular, Respiratory, Abdomen, and Other; and it will be performed at the following visits:

Baseline (Study Day 1), Week 4, Week 16, Week 28, Week 40, and Week 52/ET/ED.

The number and percentage of participants with ‘Normal’, ‘Abnormal, Not Clinically Significant (NCS)’, and ‘Abnormal, Clinically Significant (CS)’ physical exam (brief) findings will be summarized by study visits.

All brief physical examination findings will be listed.

9.5.2. Neurologic Examinations

A complete neurologic examination will be performed at the Screening visit only. All complete neurologic examination findings will only be listed.

A brief neurologic examination will include the exam categories; cranial nerves [II-XII], tone, power, deep tendon reflexes, coordination, and gait; and it will be performed at the following visits: Baseline (Study Day 1), Week 4, Week 16, Week 28, Week 40, and Week 52/ET/ED.

The number and percentage of participants with ‘normal’, ‘Abnormal’, and ‘Not Done’ neurologic exam (brief) findings will be summarized by study visits.

All brief neurologic examination findings will be listed.

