3.2.2. Safety Endpoints

The safety endpoints of this study include the following:

- Incidence of adverse events (AEs) including treatment-emergent, serious, related to study drug, and leading to withdrawal along with AEs by severity and relationship to study drug
- Mean change in clinical laboratory values from baseline to Weeks 4, 16, 28, 40, and 52
Shifts in the normality of clinical laboratory values from baseline to Weeks 4, 16, 28, 40, and 52
- Mean change in vital signs (blood pressure [supine], temperature, pulse rate) from baseline to Weeks 4, 16, 28, 40, and 52
- Mean change in body weight from baseline to Weeks 4, 16, 28, 40, and 52
- Shifts in physical exam (PE) findings from baseline to Weeks 4, 16, 28, 40, and 52
- Shifts in neurological exam (NE) findings from baseline to Weeks 4, 16, 28, 40, and 52
- Mean change in ECG parameters from baseline to Weeks 4, 28, and 52
- Concomitant medications/treatments usage
- Shifts in the C-SSRS from baseline to Weeks 4, 16, 28, 40, and 52.

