8.8. Pooling With Other Studies

Pending the outcomes of individual studies, data from Protocol PTI-125-07 may be pooled with data from Protocol PTI-125-06. These pooled analyses will include data from weeks 0 – 52 from Protocol PTI-125-06 to match the duration of Protocol PTI-125-07. Objectives and estimands for the pooled data will mirror those in Protocol PTI-125-07. Analyses will also be similar but will include an additional categorical fixed effect of study.

9. Safety and Tolerability Analysis

All safety analyses will be performed on the safety analysis set.

Safety measures including AEs, clinical laboratory values, physical examination findings, neurologic examination findings, vital signs, ECGs, and concomitant medication usage will be summarized descriptively. No inferential statistical tests will be performed, unless otherwise specified. For quantitative variables, descriptive statistics including number of observations, mean, median, standard deviation, minimum, and maximum will be presented for observed and change from baseline values at each study visit. Qualitative variables will be summarized using counts and percentages.

For all safety and tolerability analyses, participants will be analyzed by the actual treatment and dose received and, if applicable, overall.

All safety and tolerability data will be presented in participant listings.

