The observed values and changes from baseline of all quantitative safety laboratory results for clinical chemistry, hematology, and urinalysis (only for pH and Specific Gravity results) will be summarized using descriptive statistics showing the number of observations (n), mean (SD), median, minimum, and maximum value. A separate summary table with the number and percentage of participants for each categorical urinalysis parameter (glucose, protein, occult blood, ketone, nitrite, and leukocyte esterase) will be provided.

Baseline values for all clinical chemistry, hematology, and urinalysis parameters will be categorized as being below the normal range (Low), within the normal range (Normal), and above the normal range (High). Shift from baseline tables will present the number and percentage of participants who have observations that are Normal, Low, or High when such range characterizations are available. Shift tables will be presented for values shifting from Baseline (Study Day 1) to the Week 52/ET/ED.

Listings of all observed chemistry, hematology, and urinalysis laboratory data will be provided. Laboratory results outside the normal range will be flagged. The abnormal values will be flagged with 'L' (low) for values below the lower limit of the laboratory's normal range or 'H' (high) for values above the upper limit of the laboratory's normal range. Abnormal values will be graded as not clinically significant (NCS) or clinically significant (CS).

Abnormal results from the microscopic examination will be listed. All other laboratory assessments will only be listed.

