14.3.6 Other Safety Data Summary Tables		
14.3.6.1	Safety	Summary of Vital Signs Results
14.3.6.2	Safety	Summary of Weights and BMI
14.3.7.1	Safety	Summary of Concomitant Medications

Table Number	Population	Table Title/Summary
14.3.7.2	Safety	Summary of Concomitant Medications-Cognitive Enhancers Taken Prior to First Dose of Study Drug
14.3.7.3	Safety	Summary of Concomitant Medications-Cognitive Enhancers Taken Post First Dose of Study Drug
14.3.8.1	Safety	Summary of Electrocardiogram Quantitative Results
14.3.8.2	Safety	Summary of Electrocardiogram Interpretation Results
14.3.8.3	Safety	Summary of Observed Categorical ECGs
14.3.8.4	Safety	Summary of Change from Baseline Categorical ECGs
14.3.9.1	Safety	Summary of Physical Examination (Brief) Results
14.3.9.2	Safety	Summary of Neurological Examination (Brief) Results
14.3.10.1	Safety	Summary of Columbia-Suicide Severity Rating Scale (C-SSRS) Suicidal Ideation and Suicidal Behavior Experienced at Any Time Post-Treatment
14.3.10.2	Safety	Summary of Columbia-Suicide Severity Rating Scale (C-SSRS) Suicidal Ideation and Suicidal Behavior by Study Visit
14.3.10.3	Safety	Shift of Columbia-Suicide Severity Rating Scale (C-SSRS) Suicidal Ideation and Suicidal Behavior from Pre-Treatment to Post-Treatment
14.3.10.4	Safety	Shift of Columbia-Suicide Severity Rating Scale (C-SSRS) Suicidal Ideation Scores from Baseline to Treatment Period

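### SAP 3.2.2 makes shifts in physical and neurological examination findings safety endpoints, but sections 9.5.1, 9.5.2 and Table 7 plan only by-visit counts, so neither endpoint has a shift output

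*SAP*

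**What the plan says.** SAP 3.2.2 includes these two safety endpoints: "Shifts in physical exam (PE) findings from baseline to Weeks 4, 16, 28, 40, and 52" and "Shifts in neurological exam (NE) findings from baseline to Weeks 4, 16, 28, 40, and 52". It also lists shifts for laboratory normality and for the C-SSRS over the same five visits, which makes four shift endpoints.

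The analysis text for the examinations is narrower. SAP 9.5.1 gives counts and percentages for normal, abnormal not clinically significant and abnormal clinically significant, and states that "physical exam (brief) findings will be summarized by study visits". SAP 9.5.2 does the same for normal, abnormal and not done: "neurologic exam (brief) findings will be summarized by study visits". Both sections add a listing. This follows the general safety rule at the start of SAP section 9: "Qualitative variables will be summarized using counts and percentages".

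The outputs in SAP Table 7 are 14.3.9.1, "Summary of Physical Examination (Brief) Results", and 14.3.9.2, "Summary of Neurological Examination (Brief) Results". By contrast, SAP 9.2 says for laboratory values: "Shift tables will be presented for values shifting from Baseline (Study Day 1) to the Week 52/ET/ED". SAP 9.7 plans two pre- to post-treatment shift tables for the C-SSRS.

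**The concern.** A shift is a within-participant comparison: the result on Day 1 crossed with a later result. By-visit counts are the margins of that cross-classification. They include Day 1, but no planned table links a participant's Day 1 category to that participant's later category. If 9.5 is followed as written, the study report will contain two named safety endpoints without the summary that answers them.

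The question at stake is how many participants on each arm developed an examination abnormality on treatment, as distinct from carrying one in from before the first dose. In an elderly population with dementia and possible comorbidities, some abnormal findings on Day 1 are to be expected, so the distinction is worth having.

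**Working it through.** No sample size, power or alpha figure is involved. The check sets each shift endpoint in SAP 3.2.2 against the text of SAP section 9 and the output lists in SAP 13.3 to 13.5.

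| Shift endpoint (3.2.2) | Analysis text | Shift tables in Table 7 | Shift at each of Weeks 4, 16, 28, 40, 52? |
|---|---|---|---|
| Laboratory values | 9.2: Day 1 to Week 52/ET/ED | 2 (14.3.5.1.2 chemistry, 14.3.5.2.2 hematology) | No; last time point only |
| Physical examination | 9.5.1: counts by visit | 0 | No |
| Neurological examination | 9.5.2: counts by visit | 0 | No |
| C-SSRS | 9.7: pre- to post-treatment | 2 (14.3.10.3, 14.3.10.4) | No; not by week |

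**Count.** Planned shift tables: 2 + 0 + 0 + 2 = 4. Endpoints with at least one shift table: 2 of 4. Endpoints with none: 4 − 2 = 2, the two examinations. No listing or figure in 13.4 or 13.5 supplies a shift for either examination.

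**Stricter standard.** If a shift at every visit named in 3.2.2 were required, 0 of 4 endpoints would be fully met. The laboratory set is also incomplete in another way: 9.2 classifies urinalysis baselines as low, normal or high, but Table 7 lists no urinalysis shift table. The contrast therefore holds only on the test of at least one shift table.

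**Why margins are not enough (illustration only).** The documents give no prevalence of abnormal examinations, so these prevalences are assumptions. SAP 2.2 reports 804 randomized and SAP 2.4 a 1:1 ratio, so 804 / 2 = 402 per arm; take 400 with complete data and the same prevalence *p* on Day 1 and at Week 52. The number abnormal at Week 52 is 400 × *p*. If they are the same people as on Day 1, none is new; if they are all different people, all are new.

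- *p* = 5%: 400 × 0.05 = 20, so 0 to 20 newly abnormal
- *p* = 10%: 400 × 0.10 = 40, so 0 to 40
- *p* = 20%: 400 × 0.20 = 80, so 0 to 80

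The by-visit table is identical across each range. Dropout, assumed to be 20% in SAP 2.2, adds to the ambiguity because different visits then rest on different participants.

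**The case against.** The strongest reply is that this is an editorial mismatch with little consequence. Much of it stands.

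- **Other routes cover most of the ground.** Protocol 10.1 counts treatment-emergent signs, worsening of an existing abnormality and new clinically significant examination findings as adverse events, and these reach the TEAE tables by arm. Day 1 is tabulated, randomization keeps a between-arm difference in prevalence visible, and individual results are listed. What remains is mainly change that was not judged clinically significant or was not reported as an event. A reader might infer that a neurological safety signal would go unseen; the documents do not support that.
- **No protocol promise is broken.** Protocol section 4 has the examinations performed but does not name them among the measures by which safety is evaluated, and Protocol 11.4 plans no examination analysis. The inconsistency is internal to the SAP.
- **The comparators are imperfect.** A reader might infer that the laboratory and C-SSRS endpoints are fully delivered and only the examinations fall short. That is also too strong: 3.2.2 is worded more broadly than section 9 throughout.
- **Table titles are weak evidence.** The vital signs table also has a generic title, yet 9.3 says its summaries include change from baseline. The table shells are not in the documents, so a shift could sit in a shell.

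These points limit the size of the problem but do not remove it. Where the SAP intends a shift table for the other two endpoints, the text says so; 9.5 does not. Adverse event capture depends on investigator reporting and is not the endpoint named in 3.2.2. The neurological categories carry no clinical-significance grade, so that table cannot separate important abnormalities either.

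**Conclusion.** The mismatch is real and minor. Two of the four shift endpoints in SAP 3.2.2 have no planned shift output, and by-visit counts cannot stand in for one. The effect is confined to descriptive safety reporting; no test, efficacy estimate or protocol commitment is affected. No number of affected participants can be given.

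The conclusion rests on the text of 9.5.1 and 9.5.2, with the table list as support. If the shells already contain a shift, the remaining defect is that 9.5 does not say so.

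**What to change.** Add to SAP 9.5.1 and 9.5.2 one shift table per examination, by treatment received, of the Day 1 brief result against Week 52/ET/ED, the convention 9.2 uses for laboratory values.

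- **Level:** each listed body system (five) or neurological category (six), plus an overall row for any abnormality. That is (5 + 1) + (6 + 1) = 13 cross-classifications per arm.
- **Categories:** normal, abnormal NCS and abnormal CS for the physical examination; normal and abnormal for the neurological examination.
- **Missing results:** treat not done as missing, and restrict the shift to participants with both results.
- **Extra row:** participants normal on Day 1 and abnormal at any later visit. This goes beyond the laboratory convention and picks up transient findings.
- **Endpoint wording:** align the visits named in 3.2.2 with those actually tabulated.

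The cost is SAP wording and two additional tables; both brief examinations are already done on Day 1 and at every later clinic visit. Rewording 3.2.2 alone to match 9.5 would also remove the inconsistency at lower cost, but would leave new and pre-existing abnormalities unseparated in the summary tables.

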9.6. Concomitant Medications

Concomitant medications will be summarized descriptively by treatment group using the number and percentage of participants by Anatomical Therapeutic Chemical class (ATC level 2) and preferred term (ATC level 4).

All “Cognitive enhancers” defined by verbatim terms: donepezil (Aricept, Adlarity), galantamine (Razadyne, Reminyl), rivastigmine (Exelon) and memantine (Namenda, Ebixa, Nemdatine) will be summarized separately. All concomitant medication data will be listed. The cognitive enhancers will be flagged in the concomitant medication listing.

9.7. Columbia Suicide Severity Rating Scale (C-SSRS)

The C-SSRS is routinely used to quantify the presence and severity of suicidal ideation and behavior. Both the ideation and behavior subscales are sensitive to change over time.

Two versions of the C-SSRS will be used in this study: the Baseline/Screening version and the

Since Last Visit version. The Baseline/Screening version of the C-SSRS assesses lifetime suicidal ideation and behavior. The Since Last Visit version of the C-SSRS assesses suicidal thoughts or behaviors the participant may have had since the last time the C-SSRS was administered.

At the screening visit, the C-SSRS Baseline/Screening version will be administered. At all subsequent visits (Baseline, Week 4, Week 16, Week 28, Week 40, and Week 52/ET/ED), the C-SSRS Since Last Visit version will be administered.

The C-SSRS includes “yes” or “no” responses for assessment of suicidal ideation and behavior as well as numeric ratings for severity of ideation, if present (from 1 to 5, with 5 being the most severe). A score of 0 is assigned if no ideation is present.

Self-injurious behavior without suicidal intent is also a C-SSRS outcome (although not suicide-related) and has a binary response (yes/no).

Composite endpoints are defined below:

- Suicidal ideation: A “yes” answer at any time during treatment to any one of the five suicidal ideation questions (Categories 1-5) on the C-SSRS.
- Suicidal behavior: A “yes” answer at any time during treatment to any one of the five suicidal behavior questions (Categories 6-10) on the C-SSRS.
- Suicidal ideation or behavior: A “yes” answer at any time during treatment to any one of the ten suicidal ideation and behavior questions (Categories 1-10) on the C-SSRS.

Baseline is defined as the most severe ideation and behavior reported prior to the first dose of study drug (C-SSRS assessment date \leq first dose date of study drug). Suicidality data collected on the C-SSRS will be listed for all participants. Tables will include results from the Suicidal Ideation and Suicidal Behavior sections of the C-SSRS. The number and percentage of participants with a response of “Yes” at any point as well as by study visit on the Suicidal Ideation and Suicidal Behavior items will be summarized by treatment received.

Additionally, shifts of whether participants experienced suicidal ideation, behavior, or both from pre-treatment to post-treatment will be summarized in a shift table. An additional shift table of maximum ideation from pre-treatment to post-treatment will also be provided.

All C-SSRS data will be listed.

All other safety evaluations including brain MRI data, urine drug screen results, screening laboratory assessments, Genotyping results collected at Baseline (Study Day 1), and Follow-up Phone Call data will be listed.

10. Changes from Planned Analysis

Not Applicable.

11. Other Planned Analysis

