5.3. EXCLUSION CRITERIA

Subjects meeting any of the following criteria will be excluded from the study:

- 1. Residence in a skilled nursing facility requiring 24-hour care (Note subjects may reside in an assisted living facility if they do not need 24-hour care).
- 2. Any contraindications to study procedures (e.g., potential subjects with a pacemaker that is not "MRI friendly").
- 3. BMI < 18.5 or > 37.5
- 4. Evidence of a neurologic condition other than AD that, in the judgment of the Investigator, significantly contributes to the subject's dementia, including, but not limited to, frontotemporal dementia, dementia with Lewy bodies, Parkinson's disease, corticobasal degeneration, Creutzfeldt-Jakob disease, progressive supranuclear palsy, Huntington's disease, or normal pressure hydrocephalus.
- 5. Subjects with any current primary psychiatric diagnosis other than AD if, in the judgment of the Investigator, the psychiatric disorder or symptom is likely to confound interpretation of drug effect, affect cognitive assessment, or affect the subject's ability either to comply with study procedures or to complete the study. Patients with a history of schizophrenia or chronic psychosis are excluded.
- 6. Geriatric Depression Scale (15-item) score > 8 (Note a subject with a score > 8 may continue in screening if, in the judgment of the Investigator, the elevated score is not attributed to a major depressive episode).
- 7. Affirms suicidal ideation in response to questions number 4 or 5 in the C-SSRS during the past 3 months (i.e., "active suicidal ideation with some intent to act, without specific plan," or "active suicidal ideation with specific plan and intent") or affirms any of the questions contained in the Suicidal Behavior section of the C-SSRS as applicable during the past 12 months.
- 8. Meets DSM-V criteria for alcohol or substance use disorder within 2 years before the Screening Period.
- 9. MRI presence of cerebral vascular pathology (including, but not limited to, intracerebral hemorrhage, infarct > 1 cm³, > 3 lacunar infarcts, > 10 microhemorrhages, cortical superficial siderosis, diffuse confluent deep white matter hypertense lesions [Fazekas scale 3]), cerebral contusion, symptomatic subdural hematoma, or aneurysm. (Note a space-occupying lesion deemed clinically insignificant by the Investigator and confirmed by the Medical Monitor may continue screening).

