8.6. COLUMBIA-SUICIDE SEVERITY RATING SCALE (C-SSRS)

The C-SSRS¹³ is an assessment tool used to assess the lifetime suicidality of a subject (C-SSRS at baseline) as well as any new instances of suicidality (C-SSRS since last visit).

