6.1. Statistical Definitions and Algorithms

6.1.1. Baseline

The last observation recorded on or before the first dose of treatment will be used as the baseline observation for all calculations of change from baseline. In most cases, this will be the baseline visit (Day 1) pre-dose observation. In some cases, however, the baseline values may be obtained from the 60-day screening phase. For example, because MMSE is taken at screening but not at the baseline visit, the MMSE value obtained at screening will be used as the baseline value.

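### The C-SSRS shift tables use a lifetime-worst baseline, so on-treatment ideation no more severe than that lifetime worst reads as no change or improvement

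*SAP*

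**What the plan says.** SAP 9.7 gives the C-SSRS its own baseline rule: "Baseline is defined as the most severe ideation and behavior reported prior to the first dose of study drug". Of the form used at screening it says: "The Baseline/Screening version of the C-SSRS assesses lifetime suicidal ideation and behavior". Protocol 8.6 agrees, calling the scale an "assessment tool used to assess the lifetime suicidality of a subject". From Day 1 onwards the Since Last Visit form is used, which "assesses suicidal thoughts or behaviors the participant may have had since the last time the C-SSRS was administered". Ideation is scored 0 if absent and otherwise 1 to 5.

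Two shift tables rest on this baseline. Table 14.3.10.3 classifies participants by ideation, behaviour or both, before and after treatment, without a severity level. For Table 14.3.10.4 the SAP says: "An additional shift table of maximum ideation from pre-treatment to post-treatment will also be provided". SAP 3.2.2 names C-SSRS shifts from baseline as a safety endpoint.

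The general rule in SAP 6.1.1, quoted here up to its last word, is different: "The last observation recorded on or before the first dose of treatment will be used as the baseline observation for all calculations of change from". The SAP Overview also takes the most recent pre-dose value.

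On entry, Exclusion 7 (Protocol 5.3) removes a person who "Affirms suicidal ideation in response to questions number 4 or 5 in the C-SSRS during the past 3 months", or who reports suicidal behaviour within 12 months. Under Protocol 7.1.10 and SAP 9.2.1, an affirmative answer to ideation question 4 or 5 on treatment is a criterion for discontinuing study drug.

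**The concern.** The two sides of the shift cover very different periods. Participants are 50 to 87 years old, so the pre-treatment side spans decades and the post-treatment side at most 52 weeks. Exclusion 7 looks back only 3 or 12 months, so people with older severe ideation or behaviour can enrol with none at entry. If ideation then returns at or below the old level, the shift table places it on or below the diagonal.

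A shift-from-baseline safety endpoint is meant to show whether participants are worse on treatment than when they entered. For participants with a history, a lifetime maximum answers another question: whether they are worse than they have ever been. The C-SSRS tables that count any affirmative answer on treatment make no reference to baseline, so the shift tables are the only C-SSRS tables that could show change from entry.

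**Working it through.** SAP 9.7 states no figure to reproduce. The check is to list the cells of each table as the SAP defines them.

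**Inputs.** Lifetime worst ideation *b* and on-treatment worst ideation *t*, each 0-5 (SAP 9.7). Stopping level *t* = 4 or 5 (Protocol 7.1.10, SAP 9.2.1). Exclusion 7 does not bar *b* = 4 or 5 if it is older than 3 months (Protocol 5.3).

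**Table 14.3.10.4.** Read *t* > *b* as worsening, *t* = *b* as no change and *t* < *b* as improvement.

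| Cells | Total | Worsening | No change | Improvement |
|---|---|---|---|---|
| *b* = 1-5, *t* = 1-5 | 25 | 10 | 5 | 10 |
| *b* = 1-5, *t* = 4-5 | 10 | 7 | 2 (4 to 4, 5 to 5) | 1 (5 to 4) |
| *b* = 1-3, *t* = 4-5 | 6 | 6 | 0 | 0 |

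So 5 + 10 = 15 of the 25 cells with both lifetime and on-treatment ideation read as unchanged or improved. For stopping-level ideation the count is 2 + 1 = 3 of 10, and all three need a lifetime level of 4 or 5. These are counts of possible cells, not probabilities.

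**Table 14.3.10.3.** There is no severity level, so the reading follows from the categories:

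- Lifetime ideation only, on-treatment ideation only: no change, at any level including 4-5.
- Lifetime ideation and behaviour, on-treatment ideation only: looks like improvement.
- Lifetime ideation only, new behaviour on treatment: shows as a shift.

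**Direction.** The lifetime worst is never lower than the recent worst. If *t* exceeds the lifetime worst it also exceeds the recent worst, but not the reverse. The lifetime baseline can therefore hide a worsening from entry but cannot create one.

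**Against SAP 6.1.1.** Take a participant with level 4 many years ago, none reported on Day 1, and level 4 on treatment. Under SAP 6.1.1 the baseline is the Day 1 value, 0, and the shift is 0 to 4. Under SAP 9.7 the baseline is 4 and the shift is 4 to 4.

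**With a recent baseline.** Exclusion 7 bars level 4-5 ideation in the past 3 months, and Protocol 7.1.3 reconfirms eligibility on Day 1. An eligible participant's recent baseline is therefore 0-3. That gives 4 × 2 = 8 cells with *t* = 4 or 5, and all 8 read as worsening.

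**The case against.** The strongest reply is that nothing is missing from the report. SAP 9.7 defines ideation and behaviour endpoints as any affirmative answer during treatment, whatever the history. Tables 14.3.10.1 and 14.3.10.2 give these by treatment received, overall and by visit. Participants who meet a stopping criterion are counted in Table 14.3.5.4 and listed in 16.2.8.5, and all C-SSRS data are listed in 16.2.9.5. A shift table is also a cross-tabulation: a participant who reaches level 4 is counted under post-treatment level 4 whatever the baseline row. The tables are descriptive and the same rule applies to both arms.

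All of that stands, and it limits the point to how the shift tables read. It does not restore the comparison with entry status. Table 14.3.5.4, as worded, counts anyone meeting at least one criterion, pooling C-SSRS with liver and weight criteria, and gives no entry status.

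A second reply is that a scale-specific rule properly overrides a general one, and that SAP 6.1.1 applied literally would discard the screening form. That is a fair reading of intent. But SAP 6.1.1 claims all changes from baseline, and SAP 9.7 does not say that it departs from it.

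A third reply is that the recent-recall data may not exist in usable form. The 3-month recall in Exclusion 7 concerns ideation questions 4 and 5 only, and the documents do not show that recent answers to items 1-3 are stored. For behaviour, the 12-month exclusion makes a recent baseline of none nearly universal, so that part would largely repeat Table 14.3.10.1. Both limits are real. The Day 1 Since Last Visit form is scheduled for every participant and does not depend on them.

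**Conclusion.** The point holds as a limited reporting defect in a named safety endpoint, and it is worth correcting because correction is cheap. In Table 14.3.10.4, ideation at or below the lifetime worst reads as unchanged or improved, including stopping-level ideation after a lifetime level of 4 or 5. In Table 14.3.10.3, ideation without new behaviour cannot read as worse in anyone with lifetime ideation. The masking runs one way.

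Three stronger readings are tempting and are not supported:

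- That any new ideation in anyone with a remote history is hidden. In Table 14.3.10.4 a lifetime level of 1-3 followed by 4-5 reads as worsening.
- That suicidality events are lost or the comparison between arms is spoiled. The counts by treatment and the listings do not use this baseline, and the stopping criterion acts on the on-treatment answer itself.
- That a share of participants can be put on the problem. That would need an assumed prevalence of lifetime ideation and an assumed recurrence risk, neither of which is in the documents. The resulting share of emergent cases with a history would be only an upper bound on those masked, because participants who exceed their lifetime worst still show as worse.

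The conclusion rests on the SAP's description of the screening form as a lifetime assessment and on reading the shift tables in the usual way.

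**What to change.** Produce Tables 14.3.10.3 and 14.3.10.4 with a recent pre-dose baseline: the worst response on the Day 1 Since Last Visit form together with, where stored, the 3-month ideation and 12-month behaviour recall used to apply Exclusion 7. Count on-treatment ideation or behaviour above that baseline as emergent. Keep the lifetime-baseline versions as supplements, and show lifetime history as a baseline characteristic by arm. State in SAP 9.7 how its rule relates to SAP 6.1.1, so that the C-SSRS has one declared primary baseline.

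The cost is a short SAP edit and two extra descriptive tables, with no change to trial conduct. If the recall data were not stored, the recent baseline covers only the interval from screening to Day 1, at most 60 days by the schedule of activities, and the table footnotes should say so.
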